#### **A. Recruitment and Informed Consent**

We will recruit individuals from the Yale Tobacco Treatment Service (TTS) and the Winchester chest clinic. Yale TTS is a specialized outpatient service at Yale-New Haven Hospital that provides individual tobacco treatment to a large patient population of current smokers. New patients referred to the TTS will be offered the opportunity to participate in the study via clinician referrals and will provide verbal consent to be contacted by research staff. Research staff will meet with interested participants for an intake visit either remotely or in person. At the start of the intake visit, consent to participate will be obtained from all participants after the research procedures and risks associated with participation have been explained. The entire consent form will be reviewed in detail with the participant in a private, one-on-one setting with a research staff member. The consent form will provide clear and explicit language about the smoking intervention components, smoking- monitoring procedures, and smartband use. Any questions the participant may have will be addressed. If participants wish, they may take the consent form home and consider it further before signing. They may also request to speak to anyone on the research team about questions they have or to consult others, including their physician and family members. Participants will sign 2 copies of the consent, retain one, and the researchers will keep the second copy on file. Participants will be informed that they are free to decline participation and withdraw from the study at any time and that neither action will adversely affect their relationship with any study personnel. Following resolution of any questions, the participant will be asked to sign the consent form, if he/she agrees to participate.

For remote intake visits, the approved informed consent form will be provided online via Qualtrics to subjects in advance of participation. Research staff will review the consent form by phone or video conference with the potential participant, and research staff will answer any questions regarding the study or consent form at this time. Subjects who wish to participate will click "I accept" and electronically sign the document by initialing the Qualtrics form. A copy of the consent form will be automatically emailed to the participant.

## B. Protection Against Risk

The research team are trained regarding proper guidelines for ethical human research, and they will ensure that all research activities are in full compliance. All research subjects will be competent adults who willingly provide their written agreement to participate prior to research participation during a formal informed consent process. A copy of the signed consent form will be provided to all subjects. All participants will be assured that research participation is voluntary, and that even after enrollment, they are free to discontinue without penalty at any point during the study. The investigative team has decades of clinical research experience with human subjects, including conducting similar study procedures in individuals with nicotine dependence and other substance use disorders. Additional treatment referrals or continued support through the Tobacco Treatment Service will be made available to participants following study completion, as needed.

### Specific protections against risks include:

1. All personnel to be involved in this study will be certified by the Yale Human Investigation Committee (HIC) as having completed training in the protection of the rights of human subjects who participate in research.
2. Effective screening will exclude all participants who would be at greater risk for complications from smoking interventions and/or study participation because of medical or specific psychiatric illnesses. [name], a licensed clinical psychologist, will evaluate all potential participants for inclusion. If participants are not eligible for the study and/or request further assistance with quitting smoking once the study is completed, appropriate referrals will be provided.
3. Upon study enrollment, numerous safeguards will be used to monitor participants. Participants will be seen routinely during treatment by TTS staff and research team members. [name] will be available to meet with participants as needed and will provide participants with additional treatment referrals if they are interested. The TTS will be available to consult with participants and review medical concerns as needed. The TTS team consists of experts with decades of experience including: a licensed clinical psychologist who serves as the clinical director, a medical director, a pulmonologist, a team of advanced practice nurses, clinical psychology fellows, and administrative support staff.
4. Right to privacy and confidentiality for participation in this research will be protected through alphanumeric coding of data (in place of names) and proper storage of research records, including study exit interviews. Collected materials will be maintained via an alphanumeric reference system maintained by [name]. Participants' names will appear only on the consent form and a master list maintained in a physically locked file that is separate from research data. Our data collection and management procedures are fully compliant with HIPAA. Access will be limited to personnel intimately involved in the study. Participants will be informed of our efforts to maintain privacy and confidentiality. However, they will be told that if they present with suicidal or homicidal ideation and/or report any form of child/elder abuse or report plans to damage property then we will have to report this to the appropriate authorities and/or provide them with referrals for immediate treatment. Electronic data will be de-identified and password protected. Only members of the study team will have access to the physical or electronic data.

11. **Data and Safety Monitoring Plan:** Include an appropriate Data and Safety Monitoring Plan (DSMP) based on the investigator's risk assessment stated below. (Note: the HIC will make the final determination of the risk to subjects.)

- a. What is the investigator's assessment of the overall risk level for subjects participating in this study? **Minimal risk**
- b. If children are involved, what is the investigator's assessment of the overall risk level for the children participating in this study? **N/A**
- c. Include an appropriate Data and Safety Monitoring Plan. Examples of DSMPs are available here <http://your.yale.edu/policies-procedures/forms/420-fr-01-data-and-safety-monitoring-plans-templates> for
  - i. Minimal risk
  - ii. Greater than minimal

[name], the PI, will be responsible for monitoring the data, assuring protocol compliance, and conducting the safety reviews at the specified frequency that must be conducted at a minimum of every 6 months (including when reapproval of the protocol is sought). During the review process, [name] (i.e., the study monitor) will evaluate with key personnel whether the study should continue unchanged, require modification or amendment, continue or close to enrollment. [name], the Yale University IRB, and the funding agency have the authority to stop or suspend the study or require modifications.

Although we have assessed the proposed study as one of minimal risk, the potential exists for anticipated and/or unanticipated adverse events, serious or otherwise, to occur since it is not possible to predict with certainty the absolute risk in any given individual or in advance of first-hand experience with the proposed study methods. Therefore, we provide a plan for monitoring the data and safety of the proposed study.

[name] will reduce the potential for risks by being part of the screening process of all participants and reviewing eligibility criteria to rule out participants whose clinical characteristics would be adversely affected by the smoking interventions and/or participation in the research study. Frequent in-person or remote assessment and ongoing visits with treatment staff at the TTS and Winchester chest clinic will allow for close regular monitoring of participants. Research staff will check participants' data sources for clinically significant changes and alert [name] and the TTS/Winchester team as needed.

#### Attribution of Adverse Events:

Adverse events will be monitored for each individual participating in the study and attributed to the study procedures/design by [name], the PI, in collaboration with key personnel according to the following categories:

1. Definite: Adverse event is clearly related to investigational procedures(s)/agent(s).
2. Probable: Adverse event is likely related to investigational procedures(s)/agent(s).
3. Possible: Adverse event may be related to investigational procedures(s)/agent(s).
4. Unlikely: Adverse event is likely not to be related to the investigational procedures(s)/agent(s).
5. Unrelated: Adverse event is clearly not related to investigational procedure(s)/agent(s).

#### Plan for Grading Adverse Events:

The following scale will be used in grading the severity of adverse events noted during the

study:

1. Mild adverse event
2. Moderate adverse event
3. Severe

Plan for Determining Seriousness of Adverse Events: In addition to grading the adverse event, [name], the PI will determine with key personnel whether the adverse event meets the criteria for a Serious Adverse Event (SAE). An adverse event is considered serious if it:

1. is life-threatening
2. results in in-patient hospitalization or prolongation of existing hospitalization
3. results in persistent or significant disability or incapacity
4. results in a congenital anomaly or birth defect OR
5. results in death
6. based upon appropriate medical judgment, may jeopardize the subject's health and may require medical or surgical intervention to prevent one of the other outcomes listed in this definition, OR
7. adversely affects the risk/benefit ratio of the study

An adverse event may be graded as severe but still not meet the criteria for a Serious Adverse Event. Similarly, an adverse event may be graded as moderate but still meet the criteria for an SAE. [name], the PI, will consider the grade of the event as well as its "seriousness" when determining whether the event meets criteria for an SAE and requires a report to the Yale University IRB or funding agency.

#### Adverse Event Reporting:

Every event that is reported by participants to either [name], the PI, or the designated research staff and that meets criteria above will be documented. [name] will report serious adverse events and unanticipated problems to the Yale University IRB within 5 days of it becoming known using the required documentation. An adverse event report will be generated for each event and will include details of the event in the report (e.g., description of the event, when and how it was reported, as well as any official records or documentation to corroborate the event; determination of attribution). Any action resulting in a temporary or permanent suspension of this study (e.g., IRB actions, or actions by the investigators) will be immediately reported to the funding agency. [name], the PI, will conduct a review of all adverse events upon completion of every study participant with key personnel. [name] will evaluate the frequency and severity of the adverse events with key personnel and determine if modifications to the protocol or consent form are required or if a stop in protocol is required. [name] will submit an annual report summarizing all adverse events.

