Experimental Methods: Eligible participants will be randomized to one of two treatment conditions (ST vs. ST+). All participants will receive standard outpatient tobacco treatment (ST) at the Yale Tobacco Treatment Service (TTS) or Winchester chest clinic following clinical practice guidelines. All patients receive up to 8 sessions of one-on-one counseling which focuses on setting a quit date within the first 2 weeks of treatment and discusses coping strategies and relapse prevention. Patients are encouraged to try smoking cessation pharmacotherapy and can obtain these medications over the counter or by prescription from the TTS or Winchester chest clinic. The experimental group (ST+) will receive standard care plus an adjunct treatment which involves wearing a smartband for the 8-week study and receiving real-time notifications as soon as smoking is detected with the embedded geospatial movement sensors in the smartband. There are multiple commercially available smartbands/smartwatches that are compatible with the real- time smoking monitoring system; for example, the Asus Zenwatch 2 pairs with the user's smartphone via Bluetooth connection. When smoking is detected, an alert is sent to the user through the band (vibration) and their smartphone app (alert) with a message indicating that smoking was just detected. The user can indicate yes/no if this smoking detection was accurate. Real-time smoking data is recorded for the user to review in their smartphone app and is available for the research team to view on a password-protected secure online dashboard. Data include only the timing and number of smoking events, labeled by subject ID. This real-time notification may disrupt the automaticity of smoking behavior and help bring awareness to smoking and related cues in the moment, which may enhance the individual's ability to anticipate and respond adaptively to cues in the future. The control group will also receive the smartband to wear for the 8 week study to control for demands associated with remembering to wear the band and charge it.

Measures: Baseline measures will be used to characterize the sample. Repeated measures will be used to assess changes in smoking and related constructs during treatment.

Demographic Questionnaires (week 0): Age, gender, marital status, employment status, occupation.

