#### Safety and Study Progress Reviews:

[name] will lead a weekly research meeting with key personnel to review the status of all enrolled participants and discuss the eligibility of potential participants. At this weekly meeting, [name] will review study progress (i.e., recruitment goals, retention, protocol adherence). Any adverse events will be reviewed at this meeting, including serious adverse events that may have been attended to outside of this weekly meeting. An annual progress

report will be submitted to Yale University IRB and the funding agency that lists and summarizes adverse events, documents whether adverse event rates are consistent with pre-study assumptions, summarizes recruitment and retention and reason for dropouts, and summarizes study progress related to the stated aims.

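### Read literally, the adverse event logging rule covers only serious events, and neither the week 4 nor the week 8 visit asks about adverse events

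*Combined protocol and SAP*

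**What the plan says.** The logging rule stands in Section I, item 11, under Adverse Event Reporting. It begins "Every event that is reported by participants to either" the PI or the "designated research staff and that meets criteria above will be documented". An event must therefore be reported by a participant and must also meet criteria that the sentence does not name.

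Three things come before it in the same item:

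- Under Attribution of Adverse Events, five categories running from definite to unrelated, with a statement that adverse events are monitored in every participant.
- Under Plan for Grading Adverse Events, "The following scale will be used in grading the severity of adverse events noted during the" study, with levels mild, moderate and severe.
- In the same subsection, a seven-item list introduced by "An adverse event is considered serious if it".

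After the rule, the PI is to review all adverse events as each participant finishes, weigh how often they occur and how severe they are, and decide whether the protocol must be modified or stopped. The PI also "will submit an annual report summarizing all adverse events". Under Safety and Study Progress Reviews, any adverse event goes to the weekly meeting, and the annual progress report "documents whether adverse event rates are consistent with pre-study assumptions".

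On detection, the opening text of item 11 says "Research staff will check participants' data sources for clinically significant changes" and alert the PI and the clinic team. On the visits, item 4 (Measures) says "Repeated measures will be used to assess changes in smoking and related constructs during treatment".

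**The concern.** The sentence that decides what enters the adverse event record contains a filter, and the filter most naturally means serious events. The rest of the monitoring plan assumes a record of all events. Staff could follow either text in good faith and produce different data.

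The research visits might have made this harmless had they asked every participant the same question, but none of the listed measures does so. What is at stake is the completeness of the record behind the PI's periodic decisions to continue, modify or stop. The comparability of adverse event counts between the alert arm (ST+) and the control arm (ST) is also at stake.

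**Working it through.** The documents give no adverse event rate or safety threshold to reproduce, so the check is a comparison of texts and a count of scheduled measures.

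**Step 1: what the criteria are.** In the adverse event subsections before the rule, the word is used four times, all under Plan for Grading Adverse Events and each time for a serious adverse event. Attribution is by categories and severity is by a scale; neither is called criteria. Eligibility criteria appear elsewhere in the protocol but cannot be meant. No general definition of an adverse event is given.

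**Step 2: test both readings.**

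| Reading of the filter | What is logged | Fit with the rest of item 11 |
|---|---|---|
| Seriousness list | Serious events only | Conflicts with the mild and moderate grades, the review of all adverse events by frequency and severity, the annual summary of all adverse events, and the weekly review |
| Severity scale and attribution categories | Every reported event, since mild and unrelated both qualify | Consistent, but the filter then does no work |

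The first reading fits the wording and the second fits the intent. The text does not choose between them.

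**Step 3: what the visits ask.** From the list in item 4, Measures:

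- Week 4: Timeline Follow-Back, biochemical verification (when needed), craving, habit strength, perceived control, approach-avoidance task. That is 6 measures, with 0 adverse event questions.
- Week 8: the same 6, plus nicotine dependence and end-of-treatment ratings. 6 + 2 = 8 measures, with 0 adverse event questions.

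The week 8 interviews and ratings concern satisfaction and usefulness. A participant might mention a problem there, but the protocol does not describe them as a safety enquiry.

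**Step 4: other routes into the record.** Item 10 says participants are seen routinely by clinic and research staff. Item 11 promises individual monitoring, checks of data sources and a weekly status review. Section III, item 4 places the treating tobacco providers on the research team. Section IV lists cessation medication and clinic visit schedules among the research data. These are real opportunities to notice an event. None comes with a question, form or timing that makes ascertainment the same for all participants. The logging rule names the PI and designated research staff without saying whether the treating providers count among them.

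**Step 5: the comparator (secondary).** The annual progress report must set adverse event rates against assumptions made before the study. No expected rate is stated. Items 9 and 11 give only a qualitative minimal-risk assessment, and item 11 adds that absolute risk cannot be predicted with certainty.

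**The case against.** The best defence is that the serious-only reading is the less coherent one. The protocol grades mild and moderate events, treats seriousness as a further determination, gives serious events their own sentence with a 5-day IRB deadline, and then speaks of all adverse events. On that view the filter is loose drafting. This stands as an account of intent. It does not settle what staff should log, because the operative sentence still contains the filter and item 11 uses the word criteria only for serious events when it describes adverse events.

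Several stronger readings are tempting, and the documents do not support them:

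- *That events are recorded only if volunteered.* Reported by participants does not exclude answers to a question, and item 11 describes staff-initiated monitoring and weekly review.
- *That the trial would show almost no adverse events whatever happened.* Even the narrow reading records reported serious events, and monitoring may bring others to light.
- *That staff have no data to check for safety.* Timeline Follow-Back covers alcohol and other drugs, and medication use and clinic visits are recorded.
- *That events told to a clinic provider have no route to the record.* Treating providers are part of the research team; the route is unclear, not absent.

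It is also fair to say that no aim, endpoint or numeric threshold depends on adverse event rates.

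**Conclusion.** The point holds in a limited form. The logging rule, taken literally, does not require non-serious events to be documented, and this contradicts the grading, review and reporting text in the same item. With 0 adverse event questions among the 6 measures at week 4 and the 8 at week 8, non-serious events may be under-recorded and may be captured unevenly between arms. The documents give no basis for estimating how many would be missed, or for saying which arm would be more affected.

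The conclusion assumes that the list in item 4 is the complete set of visit measures and that no separate adverse event form exists outside these documents. The consequence is modest: 50 participants, a minimal-risk rating and no effect on the efficacy analyses. Small numbers (25 per arm) will limit any adverse event comparison whatever wording is used, so that limitation is not part of this point. The change is still worth making, because it alters what is recorded for the continue, modify or stop decisions at almost no cost. The missing expected rate is minor missing detail.

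**What to change.** 1. In Section I, item 11, Adverse Event Reporting, remove the filter. State instead that all adverse events, serious or not, that become known to research staff or to treating providers on the research team are logged with date, severity grade and attribution.
2. In item 4, Measures, add one open question on new or worsened health or mood problems since the last visit. Use identical wording in both arms at the existing week 4 and week 8 visits, and report the counts by arm.
3. Secondary: under Safety and Study Progress Reviews, either state the expected adverse event rate or drop the comparison with assumptions made before the study.

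The cost is a change of protocol wording, one question at two existing visits and a log entry for each event. No extra visit or staff is needed. The small downside is that more trivial events will be logged and reviewed at the existing weekly meeting.

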#### Safety and Study Progress Reviews:

[name] will lead a weekly research meeting with key personnel to review the status of all enrolled participants and discuss the eligibility of potential participants. At this weekly meeting, [name] will review study progress (i.e., recruitment goals, retention, protocol adherence). Any adverse events will be reviewed at this meeting, including serious adverse events that may have been attended to outside of this weekly meeting. An annual progress

report will be submitted to Yale University IRB and the funding agency that lists and summarizes adverse events, documents whether adverse event rates are consistent with pre-study assumptions, summarizes recruitment and retention and reason for dropouts, and summarizes study progress related to the stated aims.

